## 6.2. Patient Disposition

Disposition data will be summarized for all randomized patients. The number of patients in each analysis set population, the number of patients who discontinued study treatment including reasons, and the number of patients who discontinued the study including reasons will be summarized. The number of patients who completed the study, duration on study treatment in days and duration on study in days will also be summarized. Data will be presented overall, by study phase, and treatment group.

A by-patient listing of patient disposition data including reason for discontinuation, if applicable, will be presented for all randomized patients. A by-patient listing of randomization details will also be provided for all randomized patients.

A by-patient listing of inclusion/exclusion criteria and screen failures will be produced for all enrolled patients. Screen failures will otherwise not be included in any analyses.

## 6.3. Protocol Deviations

Protocol deviations will be identified and classified as major or minor before database lock and unblinding. Major protocol deviations may include but are not limited to:

- Violation of Inclusion/Exclusion Criteria
- Use of prohibited therapies
- Incorrect treatment

Sponsor: Boston Pharmaceuticals, Inc.  
Protocol Number: BOS161721-02  
SAP Version and Date: Version 4.0, 23Apr2021

Major protocol deviations that necessitate exclusion from the efficacy analysis in the PP population will be identified prior to database lock and unblinding.

Protocol deviations will be summarized by any deviation, deviation category, and major/minor designation. Protocol deviations will be summarized overall, by study phase, and treatment group for all randomized patients.

A listing of protocol deviations, including protocol version under which the deviation occurred, will be provided for all randomized patients. The protocol deviation listing will also include a column to indicate if the deviation resulted in the subject being excluded from the PP set based upon blinded clinical review. A separate listing of COVID-19 related deviations also will be provided.

#### 6.4. Demographic and Baseline Characteristics

Patient demographics and baseline characteristics will be summarized in the SS. These will include age (years), sex (Male / Female), ethnicity (Hispanic or Latino / Not Hispanic or Latino), race (American Indian or Alaska Native / Asian / Black or African American / Native Hawaiian or Pacific Islander / White / Other), geographic regions (North America / South or Central America / Eastern Europe), baseline height (cm), baseline weight (kg), and baseline BMI ( $\text{kg}/\text{m}^2$ ). Age is reported as collected in the clinical database and will also be categorized as a categorical variable ( $\leq 45$ ,  $> 45$ - $< 65$ ,  $\geq 65$ ) for reporting. Patient eligibility for central review will be summarized. Childbearing potential and birth control methods for female and male patients will be summarized for the DMC meetings and interim analysis only. Demographics and baseline characteristics will be summarized overall, by study phase, and treatment group.

Baseline disease characteristics will also be summarized in the FAS. The SLEDAI total score, PGA, CLASI total activity score, CLASI total damage score, ACR-28 sum of swelling, ACR-28 sum of tenderness, ACR-28 sum of active joints (swelling and tenderness in the same joint) and SLICC/ACR damage index total score will be summarized at baseline. Frequencies and percentages of patients with SLEDAI presence by component, ACR-28 loss of functional range interfering with life and ACR-28 impairment of basic activities from inflammation as well as BILAG grades by body organ system will be presented. Frequency and percentage of patients with each organ system disease on BILAG SLE history will be summarized. Frequency and percentage of patients with SLICC criteria for SLE will be summarized. Frequencies and percentages of patients with CLASI Activity Score ( $< 8$  vs.  $\geq 8$ ), SLEDAI-2K ( $< 10$  vs.  $\geq 10$ ) and baseline corticosteroid use (0,  $< 7.5$ ,  $\geq 7.5$ ,  $< 10$ ,  $\geq 10$  mg/day), will be presented. In case of missing data, LOCF methods consistent with the primary efficacy analysis described in Section 7.1 will be used for baseline disease characteristics summaries.

Frequencies and percentages of patients will also be presented for the following characteristics:

- Positive anti-ds-DNA
- Low C3 and/or C4

Sponsor: Boston Pharmaceuticals, Inc.  
Protocol Number: BOS161721-02  
SAP Version and Date: Version 4.0, 23Apr2021

- Positive anti-dsDNA and normal C3 and normal C4
- Negative anti-dsDNA and low C3 and/or C4
- Positive anti-dsDNA and low C3 and/or C4
- Negative anti-dsDNA and normal C3 and normal C4
- Other

In addition, frequencies and percentages of patients will be presented for the following characteristics:

- SLEDAI-2K  $\geq$  10 and negative\*\* anti-dsDNA and normal C3 and normal C4
- SLEDAI-2K  $\geq$  10 and positive\*\* anti-dsDNA and normal C3 and normal C4
- SLEDAI-2K  $\geq$  10 and negative\*\* anti-dsDNA and low C3 and/or C4
- SLEDAI-2K  $<$  10 and positive\*\* anti-dsDNA and low C3 and/or C4
- SLEDAI-2K  $<$  10 and positive\*\* anti-dsDNA and normal C3 and normal C4
- SLEDAI-2K  $<$  10 and negative\*\* anti-dsDNA and low C3 and/or C4
- SLEDAI-2K  $<$  10 and negative\*\* anti-dsDNA and normal C3 and normal C4
- SLEDAI-2K  $\geq$  10 and positive\*\* anti-dsDNA and low C3 and/or C4

\*\* Positive anti-dsDNA is defined as  $\geq$  15 IU/mL. Negative anti-dsDNA is defined as  $<$  15 IU/mL

Time from diagnosis to informed consent in years defined as (informed consent date - date of diagnosis as recorded on the screening BILAG assessment)/365.35 will be summarized. Partial dates of diagnosis will be handled as defined in section 5.5. Baseline disease characteristics will be summarized overall by study phase and treatment group.

Demographics and baseline characteristics will be listed for all randomized patients. A separate by-patient listing will be created for childbearing potential and birth control for all randomized patients.

The following conversions and equations will be used as applicable:

Height (in cm) = height (in inches) \* 2.54

Weight (in kg) = weight (in lbs) \* 0.4536

BMI (kg/m^2) = weight(kg)/[height(m)]

## 6.5. Medical History

The incidence of medical history will be summarized by system organ class (SOC) and preferred term (PT) overall, by study phase, and treatment group in the SS. Patients will be counted once per SOC (likewise for PT within SOC). Medical history terms will be coded based on the Medical Dictionary for Regulatory Affairs (MedDRA). Medical history will be reported in

Sponsor: Boston Pharmaceuticals, Inc.  
Protocol Number: BOS161721-02  
SAP Version and Date: Version 4.0, 23Apr2021

descending order of overall incidence of SOC and then in descending order of overall incidence for PT within the SOC.

Medical history will be presented in data listings for all randomized patients. Medical history coded terms will be provided, including the SOC and PT.

The MedDRA version used is defined in the study data management plan.

## 6.6. Prior and Concomitant Medication and Procedures

The incidence of medication use will be summarized by World Health Organization (WHO) Drug Dictionary anatomic therapeutic class (ATC) Level 2 classification (i.e. therapeutic main group) and preferred name. A patient will be counted only once at each level of reporting. Prior medications are those which have been identified to have been discontinued prior to the first dose of study medication. Concomitant medications are those which have been identified to have been taken at any point during the period of time between the first dose of study drug and last dose of study drug + 90 days, including medications which started prior to first dose of study drug that are ongoing at first dose. Subsequent medications are those which have been started after the last dose date + 90 days. The data management plan specifies the version of WHO Drug used.

Partial dates will be imputed according to Section 5.5 for the determination of prior, concomitant, and subsequent medications.

Concomitant medication use will be summarized and presented overall, by study phase, and treatment group in the SS.

A separate summary will be prepared for corticosteroids. Corticosteroids will be presented overall, by study phase and treatment group in the SS. The average daily dose of CS (prednisone equivalent) at each visit including summary statistics as well as categorical summaries for <5 mg/day,  $\geq 5$  mg/day to  $\leq 10$  mg/day, and  $> 10$  mg/day and for dosages of interest relevant to Phase 2, i.e. 0 mg/day,  $< 7.5$  mg/day,  $\geq 7.5$  mg/day, and for dosages of interest to Phase 1b, i.e.  $< 10$  mg/day, and  $\geq 10$  mg/day will be presented. Average daily dose is calculated as described in Section 7.2.4. Prednisone equivalence is also provided in the same section.

All prior and concomitant medication data will be provided together in a by-patient listing including the verbatim and preferred drug name and WHO ATC Class (ATC Level 2) for all randomized patients. Past biological, immunosuppressant, antimalarial and corticosteroid SLE medication history data will be listed separately for all randomized patients.

Concomitant procedures will be presented in a data listing for all randomized patients.

## 6.7. Study Drug Exposure and Compliance

The total dose administered (mL) and the number of doses received will be summarized as continuous variables. The number and percentage of patients that received any dose and the number and percentage of patients who received the total planned dose at each nominal, protocol specified, visit (Day 0 / Day 30 / Day 60 / Day 90 / Day 120 / Day 150 / Day 180) will be summarized. The number and percentage of patients who received 1-7 doses (mutually exclusive) will also be summarized categorically. The denominator for the number of patients dosed and the number of doses received will be the number of patients in the SS. The denominator for the number of patients who received the total planned dose will be the number of patients dosed at the corresponding nominal visit.

The percent compliance will be summarized descriptively and is defined as  $100 * (\text{sum of doses received} / 7)$ . Percent compliance will also be calculated categorically as  $<70\%$ ,  $\geq 70\%$  to  $<85\%$ ,  $\geq 85\%$  to  $<100\%$ ,  $\geq 100\%$ .

Relative dose intensity will be summarized descriptively and is defined as  $100 * (\text{total actual dose summed across all visits} / \text{total planned dose summed across all planned visits})$  per the below table.

| Dose Level (mg) | Dose Level (mL)* | Total Planned Dose Across All 7 Visits (mL) | Relative Dose Intensity Calculation                                      |
|-----------------|------------------|---|--|
| 20              | 0.4              | 2.8   | $(\text{Total actual dose in mL summed across all visits} / 2.8) * 100$  |
| 60              | 1.2              | 8.4   | $(\text{Total actual dose in mL summed across all visits} / 8.4) * 100$  |
| 120             | 2.4              | 16.8  | $(\text{Total actual dose in mL summed across all visits} / 16.8) * 100$ |

\* Dose Level in mL is based on 50mg/mL administration.

The duration of exposure in days will also be summarized descriptively and is defined as the last dose date – first dose date +1.

Study drug exposure and compliance will be presented overall, by study phase, and treatment group in the SS.

By-patient listings of BOS161721 and placebo dosing data will be produced for all patients in the SS.

## 7. EFFICACY

### 7.1. Primary Efficacy Endpoint and Analyses

Safety will be the primary endpoint for the Phase 1b MAD portion of the study and is discussed in Section 10. Efficacy will be evaluated for the Phase 1b MAD portion of the study as an exploratory endpoint and details will be included in relation to the Phase 2 POC portion of the study within this section. Efficacy analyses will be presented by study phase and treatment group.

#### 7.1.1. The proportion of patients with a SRI-4 response at Day 210

The primary efficacy endpoint for the POC is the proportion of patients who achieve a SRI-4 response at Day 210 in the FAS.

The SRI-4 is a composite index of SLE disease improvement that consists of scores derived from the SLEDAI-2K, the BILAG 2004 Index, and the PGA. SRI-4 response is defined as:

1)  $\geq$  4-point reduction from baseline in SLEDAI-2K total score

AND

2) No new severe disease activity (BILAG A organ score) or more than 1 new moderate organ score (BILAG B) compared with baseline

AND

3) No deterioration from baseline in the PGA by  $\geq$  30mm.

The test for treatment group difference in proportion of patients who achieve a SRI-4 response at Day 210 will be based on Pearson's chi-square test. The difference in percentages of patients who achieve SRI-4 response (BOS161721 vs. Placebo) will be presented with its corresponding (Wald) 90% CI. The number and percentage of SRI-4 responders, along with an exact (Clopper-Pearson) 90% CI, will be presented by treatment group. If an expected count for the Pearson chi-square test falls below 5, a Fisher's exact test will be used to assess the treatment difference and the CI will be based on an exact method (Santner Snell). The analyses will be repeated for each of the three components contributing to the SRI-4 response. The primary analysis of the primary efficacy endpoint will be performed in the FAS and presented by treatment group. The analysis will be repeated in the PP analysis set. SRI-4 Response at Day 210 will also be repeated by all subgroups in Section 4.2 and treatment group for POC Phase 2 only.

The superiority of BOS161721 relative to placebo will be evaluated. If the proportion of SRI-4 responders for the selected POC dose in BOS161721 arm is higher than that of the POC placebo

arm, then BOS161721 will be considered superior to placebo if the 2-sided p-value is less than 0.10.

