### 3.3. Sample Size Considerations

Sample size in the Phase 1b part of the study is based on operational consideration.

The sample size in the Phase 2 POC study is based on the primary endpoint, SRI-4 Response at Day 210. Based on efficacy data from a recently completed study with Ustekinumabiii, where the primary endpoint was also SRI-4, the sample size in the phase 2 part of the BOS161721-02 study is set at 96 evaluable patients. In the Ustekinumab study of 102 patients, a statistically significant difference in SRI-4 response was shown in favor of Ustekinumab (62% of Ustekinumab treated patients achieved SRI-4 response vs. 33% in patients receiving placebo). The Ustekinumab phase 2 study is an appropriate comparator to BOS161721-02 because both studies share the same primary endpoint of SRI-4 response and BOS161721 and Ustekinumab have overlapping mechanisms of action (T follicular helper and Th17 cell biology).

Sponsor: Boston Pharmaceuticals, Inc.  
Protocol Number: BOS161721-02  
SAP Version and Date: Version 4.0, 23Apr2021

Approximately 110 additional patients will be randomized in a 2:1 ratio to BOS161721 versus placebo to achieve approximately 96 evaluable patients in the FAS of the phase 2 portion. This assumes 14 patients will discontinue prior to having received treatment or having completed a post-baseline efficacy measure. Enrollment and randomization will be monitored in a blinded fashion and may be increased if needed to ensure at least 96 evaluable patients are randomized into the FAS (see Section 6.1).

A total of 96 evaluable patients randomized provides 80% power to detect a treatment difference of 29% in SRI-4 response rates at Day 210, based on a targeted 2-sided significance level of 10% and using a 2-sided Pearson's chi-squared test. This assumes a response rate of 62% for BOS161721 and 33% for placebo.

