#### 4.1. Stratification and Covariates

[figure not shown]
The effects of noncompliance, background therapy use, treatment discontinuations, premature withdrawal from study and covariates will be assessed to determine the impact on the general applicability of results from this study. Exploratory analyses of the data may be conducted as deemed appropriate to evaluate factors for which analyses are not controlled.

Continuous efficacy endpoints will be assessed via analysis of variance (ANOVA) or analysis of covariance (ANCOVA) when applicable, adjusting for the baseline value.

Sensitivity analyses of the primary efficacy endpoint may be performed with covariates defined based on the subgroups in section 4.2.

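### The primary SRI-4 test is valid but unadjusted; pre-specifying adjustment for baseline SLEDAI-2K would cost little and could gain up to about 7 points of power

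*SAP*

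**What the plan says.** In SAP Section 7.1.1 the superiority decision rests on one comparison: the treatment difference "in proportion of patients who achieve a SRI-4 response at Day 210 will be based on Pearson's chi-square test", with superiority declared at a two-sided p below 0.10. Fisher's exact test replaces it if an expected count falls below 5. The reported effect is a difference in percentages with a Wald 90% CI. The same section describes SRI-4 as a "composite index of SLE disease improvement that consists of scores derived from the SLEDAI-2K, the BILAG 2004 Index, and the PGA". Its first condition is a SLEDAI-2K reduction of at least 4 points, and the BILAG and PGA conditions must hold as well. Medication failures and early withdrawals count as non-responders.

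Section 3.2 randomises separately by study portion and cohort and names no other factor. On covariates, Section 4.1 says only: "Sensitivity analyses of the primary efficacy endpoint may be performed with covariates defined based on the subgroups in section 4.2". Table 2 in Section 7.1.1 lists a logistic regression as Sensitivity Analysis 4, among analyses introduced as ones that may be done; its content is redacted.

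Baseline SLEDAI-2K is available for everyone concerned. It is the covariate in the ANCOVA of SLEDAI-2K change (Section 7.2.10.2), and a patient without pre-treatment SLEDAI-2K, PGA or BILAG leaves the primary analysis (Section 7.1.1, Missing Data).

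**The concern.** A 4-point fall is plausibly easier to reach from a high starting score than from a low one. If so, part of the variation in response is explained by a value already in the database, and a test that does not use it is less sensitive than it could be. The placebo arm has about 32 evaluable patients and randomisation is not stratified on disease activity, so the arms can differ in baseline score by chance, and the decision test cannot correct for that. The SAP binds nobody to an adjusted result for the endpoint that decides the trial. At stake is some power, and how far the conclusion depends on the luck of one randomisation. Validity is not at stake.

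**Working it through.** **Inputs from SAP Section 3.3.** Sample size and power: "A total of 96 evaluable patients randomized provides 80% power to detect a treatment difference of 29% in SRI-4 response rates at Day 210". Test and level: "based on a targeted 2-sided significance level of 10% and using a 2-sided Pearson's chi-squared test". Rates: "This assumes a response rate of 62% for BOS161721 and 33% for placebo". Allocation: "Approximately 110 additional patients will be randomized in a 2:1 ratio to BOS161721 versus placebo". With 2:1 allocation, 96 evaluable patients are 64 active and 32 placebo.

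**Step 1: the plan's own figure.**
- Pooled rate = (32 × 0.33 + 64 × 0.62)/96 = 0.523.
- SE under the null = √[0.523 × 0.477 × (1/32 + 1/64)] = 0.108.
- SE under the alternative = √[0.33 × 0.67/32 + 0.62 × 0.38/64] = 0.103.
- Continuity correction = 0.5 × (1/32 + 1/64) = 0.0234.
- Power with the correction = Φ[(0.29 − 0.0234 − 1.645 × 0.108)/0.103] = 80.6%. The continuity-corrected sample-size formula returns exactly 32 + 64 = 96.
- Power without the correction, which is the Pearson test as named = Φ[(0.29 − 1.645 × 0.108)/0.103] = 86.2%; exact enumeration gives 85.8%.

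So 96 at 80% reproduces, and the named test does better than stated.

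**Step 2: the missing input.** The documents give no association between baseline SLEDAI-2K and SRI-4. Assumed range: odds ratio per SD of baseline from 1.0 to 3.0, which corresponds to a within-arm correlation r from 0 to 0.43.

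**Step 3: simulated power with adjustment.** 64/32 patients, standard-normal baseline linear on the logit, marginal rates held at 62% and 33%, two-sided 10%. The chi-square, likelihood-ratio and CMH columns use 4,000 trials per row; the score-test column uses 40,000 and was run for the three stronger settings only.

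| r | OR per SD | Chi-square | Logistic, likelihood ratio | Logistic, score test | CMH, two strata |
|---|---|---|---|---|---|
| 0 | 1.0 | 85.5% | 85.7% | – | 85.3% |
| 0.11 | 1.25 | 84.9% | 86.2% | – | 85.4% |
| 0.19 | 1.5 | 85.2% | 87.1% | 87.0% | 86.4% |
| 0.30 | 2.0 | 86.1% | 89.9% | 89.3% | 88.5% |
| 0.43 | 3.0 | 85.0% | 91.9% | 91.7% | 89.4% |

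The chi-square column differs between rows only by simulation error: √(0.86 × 0.14/4000) is about 0.5 points, around the exact 85.8%.

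**Step 4: closed-form cross-check.** Multiply both variances by (1 − r²). Power is 86.5%, 87.4%, 89.0% and 91.1% at r = 0.1, 0.2, 0.3 and 0.4. The equivalent unadjusted sample size is 96/(1 − r²) = 97, 100, 105.5 and 114.3, a gain worth about 1 to 4 patients at r of 0.1 to 0.2 and about 10 to 18 at 0.3 to 0.4.

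**Step 5: a smaller effect.** If the true rates were 55% and 33% (assumed), unadjusted power would be about 65-66%, and the score test would have 67.5%, 70.1% and 74.1% at odds ratios 1.5, 2 and 3.

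**Step 6: type I error.** With both rates at 33%, the likelihood-ratio test rejected in 10.0-11.1% of trials and the chi-square in 9.5-10.8%. In the larger runs the score test rejected in 10.3-10.6% and the chi-square in 10.2-10.3%.

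**Step 7: chance imbalance.** The SE of the difference in baseline means is √(1/64 + 1/32) = 0.217 SD, so an imbalance of 0.25 SD or more in either direction arises in about 25% of trials. At an assumed odds ratio of 2, with higher scores favouring response:
- Active arm lower by at least 0.25 SD, at 62% vs 33%: chi-square power falls to about 72%; adjusted power stays at about 89%.
- Active arm higher by at least 0.25 SD, no drug effect: the chi-square declares superiority in about 11% of such trials and the adjusted test in about 5%, which is the nominal rate in that direction.

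These are conditional figures. Over all randomisations the chi-square keeps its 10% level.

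**The case against.** The strongest reply is that nothing here is wrong. An unadjusted chi-square in a randomised trial is valid and fully specified, and it is the same test that Section 3.3 uses for power. That stands, and it is why this is offered as an improvement. Other points also stand:

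- The gain is assumed. At the weak end of the range it is 0 to 2 points, and the 92% figure needs an odds ratio of 3 per SD.
- SRI-4 is a three-part composite with non-response imputation. A reader might treat it as simply a change in SLEDAI-2K, but the BILAG and PGA conditions and the handling of medication failures and withdrawals may all weaken the link to the baseline score.
- A reader might infer that the SAP ignores baseline disease activity. It does not. The Day 210 analysis will be repeated by the Section 4.2 subgroups, whose readable text refers to baseline CLASI and SLEDAI; Section 6.4 tabulates SLEDAI-2K below and above 10; and the redacted logistic analysis may contain it.
- A reader might also infer that every continuous endpoint is baseline-adjusted and the primary is the odd one out. Duration of longest SRI-4 response uses ANOVA with treatment alone (Section 7.2.13), and the other responder endpoints follow the same Section 7.1.1 methods.

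None of this removes the gain that is available if baseline is prognostic. If it is not, the simulations show essentially no loss.

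**Conclusion.** The point holds as an efficiency and robustness improvement. Under the SAP's rates, adjustment moves power from about 86% to 86-87% for r up to 0.2, to 89-90% at 0.3 and to about 92% at 0.43, with type I error of about 10-11%. It also protects the decision against chance baseline imbalance. These sizes rest on an assumed prognostic strength, a normal baseline that is linear on the logit, and 64/32 evaluable patients.

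The tempting stronger reading is that this choice leaves the trial underpowered. The documents do not support it: the named test exceeds the stated 80% under the SAP's own assumptions.

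**What to change.** Before unblinding, amend Section 7.1.1 and the primary row of Table 2:

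- Primary test: logistic regression with treatment and continuous baseline SLEDAI-2K, with the score test for treatment at two-sided 0.10. State that this test governs the superiority decision.
- Effect estimate: the standardised risk difference from the same model with a 90% CI and a named variance method, so that the effect measure stays a difference in proportions.
- Supportive analysis, and pre-specified fallback if the model does not converge: the Pearson chi-square with Wald CI as now written.
- Section 3.3: note that the power statement refers to the unadjusted test, and that 96 corresponds to a continuity-corrected calculation.
- Secondary and subgroup analyses that borrow the Section 7.1.1 methods: say whether they keep the Pearson test.

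The cost is SAP wording, an entry in Section 11 if the protocol names the chi-square, and a model-based primary result in place of a 2×2 table. No patients are lost, because those without a pre-treatment SLEDAI-2K are already excluded. If the sponsor prefers to keep the chi-square as primary, the least change is to make this adjusted analysis a firm supportive one instead of an optional one.

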## 4. DATA ANALYSIS CONSIDERATIONS

All analyses will be conducted based on SAS 9.3 or higher.

All data in the database will be presented in by-patient data listings.

Unless otherwise stated, all listings will be sorted by study phase, treatment group, patient number, and assessment date (and time, if available). If assessment date is missing, chronological visit will be used for sorting.

Unless stated otherwise, continuous data will be summarized by treatment group based on number of patients (n), mean, median, standard deviation (SD), 25th percentile/first quartile (Q1), 75th percentile/third quartile (Q3), minimum value, and maximum value.

The geometric % coefficient of variation (CV) is calculated as  $100 * \sqrt{\exp(SD\log^2) - 1}$  where SDlog is the SD of log-transformed values.

Unless stated otherwise, categorical data will be summarized by treatment group using n and percentage based on the number of non-missing values.

- The number of missing values will be presented as a separate category with no percentage, but only if one or more patients are missing data.
- Counts of zero will be presented without percentages.

Sponsor: Boston Pharmaceuticals, Inc.  
Protocol Number: BOS161721-02  
SAP Version and Date: Version 4.0, 23Apr2021

Statistics will be presented in the summary tables based on the following:

- Minimum and maximum: same number of significant digits as the raw value
- Mean, median, Q1, and Q3: one additional decimal place to that reported for minimum and maximum
- SD: two additional decimal places than presented for the minimum and maximum
- Percentages: reported to one decimal place with the exception of 100% which will be displayed without decimals.
- P-values will be reported to four decimal places. If the value is below 0.0001 it will be noted as < 0.0001; if the value above 0.9999 it will be noted as > 0.9999.

Unless otherwise noted, statistical inference will be based on a 10% significance level (i.e. 90% confidence intervals will be produced).

Statistical testing will be performed on data from the Phase 2 study.

Numbering for data displays will be based on ICH E3.

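### The Wald 90% interval for the primary SRI-4 difference slightly under-covers and can disagree with the Pearson test on zero, in either direction; the superiority decision is not affected

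*SAP*

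**What the plan says.** SAP Section 7.1.1 states that the treatment comparison of SRI-4 response "at Day 210 will be based on Pearson's chi-square test". The difference in percentages "will be presented with its corresponding (Wald) 90% CI". BOS161721 is declared "superior to placebo if the 2-sided p-value is less than 0.10" and its response rate is the higher one. There is one fallback: "If an expected count for the Pearson chi-square test falls below 5, a Fisher's exact test will be used to assess the treatment difference". In that case an exact interval (Santner-Snell) replaces the Wald one.

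Section 4 links test level and interval level for the whole plan: "statistical inference will be based on a 10% significance level (i.e. 90% confidence intervals will be produced").

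Section 3.3 gives the planning figures: "A total of 96 evaluable patients randomized provides 80% power"; "This assumes a response rate of 62% for BOS161721 and 33% for placebo"; 2:1 allocation.

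The same test and interval are carried by cross-reference to SRI-4, SRI-5 and SRI-6 by visit (7.2.1 to 7.2.3), sustained corticosteroid reduction in the POC part (7.2.4.2), BILAG flares (7.2.5), PGA worsening (7.2.6.1), BICLA (7.2.7), CLASI response (7.2.8.1), SLEDAI-2K response (7.2.10.1) and medication failure (7.2.12.1). Section 7.1.1 also repeats the primary analysis by subgroup.

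**The concern.** Pearson's statistic divides the observed difference by a standard error computed under equal rates (pooled). The Wald interval uses the two observed rates separately (unpooled). With equal arms the unpooled standard error never exceeds the pooled one. With 2:1 allocation either can be the larger, depending on where the rates lie. A 90% Wald interval is therefore not the inversion of the 10% Pearson test, although Section 4 presents them as a pair.

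Two things follow. The interval in the primary table may not have its stated 90% coverage. And in a borderline trial the table could show a non-significant p-value beside an interval that excludes zero, or a significant one beside an interval that includes it. The SAP does not say how such a row should be read.

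**Working it through.** **Inputs.** Two-sided alpha 0.10, 96 evaluable patients, 62% and 33%, 2:1 (Section 3.3); Pearson test, Wald interval, fallback when an expected count is below 5 (Section 7.1.1). The split 64:32 is derived from 96 at 2:1 and is not written in the SAP. z = 1.645.

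**The plan's own figure first.** Mean rate = (2 × 0.62 + 0.33)/3 = 0.5233. Placebo n without continuity correction:

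[1.645 × √(1.5 × 0.5233 × 0.4767) + 0.8416 × √(0.62 × 0.38/2 + 0.33 × 0.67)]² / 0.29² = 26.6, so 27 placebo and 81 in total.

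With the continuity correction: (26.6/4) × [1 + √(1 + 6/(26.6 × 2 × 0.29))]² = 31.6, so 32 placebo and 96 in total. The plan's 96 is therefore reproduced, with 64:32. (Without the correction, 64:32 has about 86% power; that is a separate matter.)

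**Formulas for the check.** For x responders of 64 and y of 32, with p1 = x/64, p2 = y/32, d = p1 − p2:

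- Wald limits: d ± 1.645 × √[p1(1 − p1)/64 + p2(1 − p2)/32]
- Pearson: z = d / √[p(1 − p)(1/64 + 1/32)], with p = (x + y)/96

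Coverage and disagreement are sums of product-binomial probabilities over all 65 × 33 = 2,145 tables. Disagreement is counted only in the 1,905 tables where every expected count is at least 5, because only there does the SAP use this pair.

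**Coverage at 64:32.**

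| Active / placebo | Wald 90% coverage |
|---|---|
| 62% / 33% | 88.6% |
| 50% / 33% | 89.0% |
| 48% / 33% | 88.7% |
| 33% / 33% | 88.9% |
| 50% / 50% | 89.9% |

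Over both rates from 20% to 80% in steps of 2 points, coverage runs from 87.8% to 89.9% (mean 89.0%). The Mee score interval covers 90.1% at 62%/33% and averages 89.8% on the same grid.

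**Why it under-covers.** At 33%/33% the Wald interval excludes zero in 11.1% of trials: it lies wholly above zero in 6.3% and wholly below in 11.1 − 6.3 = 4.8%, against a nominal 5% on each side. The excess is on one side, so the interval sits too high.

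**A disagreement in one direction.** 31/64 versus 10/32: d = 0.4844 − 0.3125 = 0.1719.

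- Unpooled SE = √(0.4844 × 0.5156/64 + 0.3125 × 0.6875/32) = 0.1030; limits 0.1719 ± 0.1695, that is +0.2 to +34.1 points.
- Pooled p = 41/96 = 0.4271, SE = 0.1071, z = 1.605, p-value 0.1085.
- Smallest expected count = 41 × 32/96 = 13.7, so the fallback is not triggered.
- Mee limits: −0.4 to +33.0 points. Width 33.4 points, against 34.1 − 0.2 = 33.9 for Wald.

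**And in the other.** 45/64 versus 17/32: d is again 0.1719. Unpooled SE 0.1051 gives −0.1 to +34.5 points; pooled SE 0.1035 gives z = 1.660, p-value 0.0969. The Mee lower limit is about +0.2, in agreement with the test.

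**How often.** The Wald interval excludes zero with p at or above 0.10 in 14 tables, 7 of them favouring BOS161721. The reverse occurs in 8 tables, 4 of them favouring BOS161721. With 33% placebo response the probability of the first kind is:

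| Active response | Probability |
|---|---|
| 62% | 0.16% |
| 53% | 1.8% |
| 50% | 2.5% |
| 48% | 2.8% |
| 33% | 1.3% |

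The largest value on the grid is 5.5% (34%/20%). The figure is sensitive to the realised split: at 62:34 it is close to zero for 48% and 53% against 33%, while coverage stays below 90% (about 88.9%).

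**The case against.** The case against acting is respectable. Pearson with a Wald risk-difference interval is a fully specified and common large-sample pairing. The decision rule names the p-value only, and the interval is merely displayed. Section 4 can be read as setting a confidence level without promising that test and interval will always agree. The coverage shortfall is 1.4 points at the planned rates and at most about 2 on the grid, and a limit of +0.2 beside p = 0.1085 would mislead few careful readers. Smaller tables are partly protected by the switch to Fisher and an exact interval. All of this stands, and it limits the point to low severity.

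Three stronger readings are tempting, and the documents support none of them.

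- **That the Wald interval is too short and so overstates precision.** In the worked example it is wider than the score interval (33.9 against 33.4 points). The fault is mainly where the interval sits.
- **That the trial could reach the wrong conclusion, or that its type I error is inflated.** Superiority is decided by the Pearson p-value, which the interval does not touch.
- **That the mismatch always flatters the drug.** It runs both ways, as 45/64 versus 17/32 shows.

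Nor can the effect on subgroups be sized from the SAP, because their definitions are redacted.

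What the objection does not answer is that the mismatch arises only in borderline results, where readers look hardest at the interval, and that it can be avoided at almost no cost. The exact fallback does not help in the primary analysis, because at the planned rates an expected count below 5 has practically zero probability.

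**Conclusion.** The point holds at low severity. At 64:32 the Wald 90% interval for the primary difference covers about 88% to 90% over response rates of 20% to 80%, and 88.6% at the planned rates. It can disagree with the Pearson test on zero in either direction. An interval excluding zero without significance is rare at the planned effect (0.16%) and reaches about 1% to 3% at smaller effects with 33% placebo response. It is more likely at lower placebo rates.

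These figures assume the derived 64:32 split and independent binomial responses; another split changes the disagreement rate considerably but leaves coverage below 90% in the alternative checked (62:34). Only the displayed interval is affected. The same pair is displayed for the binary secondary endpoints and the subgroups unless an expected count is below 5.

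**What to change.** In Section 7.1.1, replace the Wald 90% interval for the difference in response rates with the 90% score interval that inverts the Pearson statistic (Mee form), and let the existing cross-references carry it to the secondary endpoints and subgroups. The Mee form agrees with the Pearson test on zero by construction. Miettinen-Nurminen is nearly identical (−0.5 to +33.1 points in the first example, against −0.4 to +33.0) and would also serve, though its small variance factor means that agreement is not exact.

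Leave unchanged the Pearson decision rule, the Clopper-Pearson intervals for each arm, and the Fisher/Santner-Snell fallback.

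The cost is one phrase in the SAP and one option in the program, with no effect on sample size or error rate. Lower limits will typically be about 0.5 to 1 point less favourable to BOS161721 (0.7 points in the first example: +0.24 to −0.44). Where the mismatch runs the other way, the lower limit rises slightly.
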